**FIGURE 1: STUDY DIAGRAM**

## INVESTIGATIONAL PLAN

### General Schema of Study Design

#### 3.1.1 Screening Phase

Participants in the CHOP care network will be mailed/e-mailed a letter inviting them to participate in the study. Interested participants can contact the study team using a dedicated e-mail address and phone number. Participants will verbally complete our eligibility screening survey over the phone with a study team member. The solicited information from the eligibility screening survey will be limited to the minimum necessary (e.g., just the inclusion/exclusion criteria) for screening/determining eligibility for the main study and the screening will be brief in duration. Therefore, consent does not apply.

#### 3.1.2 Study Treatment Phase

Eligible participants will be asked to verbally consent to study procedures over the phone. Verbal consent will be documented in REDCap. Once the participant is enrolled, they will be allocated to either the control or intervention group. A research assistant will send the participant an invitation to complete the Intake Survey via REDCap prior to the study visit. If participants have not completed this intake survey prior to their study visit, they will be asked to complete the survey in-person before moving on to the intervention phase.

There will be a one-time study visit, which will take place in a study room on the 4th floor of the Roberts Center for Pediatric Research. The intervention phase of the visit will take place in a study room on the 4th floor.

A member of the study team will meet the participant in the Roberts Center for Pediatric Research parking lot or lobby. The study team member will escort the family to the 4th floor study room. Next, the team member will explain the click tight car seat system and demonstrate it to the participant. The participant will then be asked to do a full install of the car seat prior to completing the misuse scenarios. The participant will then be asked to complete three misuse scenarios. Participants in the intervention group will use the app while participants in the control group will complete the scenarios without the app.

Misuse scenarios will be evaluated by a member of the study team, including measuring harness tightness with a load cell and the pinch test (this will be a yes/no formatted question indicating whether the harness passed the slack test) and asking the participant to see the app once they are finished the scenario. In addition, after each misuse scenario is complete, participants will be asked to complete a brief survey about their experience. Participants will also complete a brief interview at the end of their study visit to understand more about their preferences.

While the first 10 or fewer participants are enrolled, all of the above study procedures will be evaluated to understand any complications of using the prototype convertible child safety seat or collecting data that we may have not predicted (e.g., not understanding how to read the indicator lights). Therefore, we will be monitoring incoming data closely over the first few weeks of the study. If any complications related to the technology or data collection methods arise, we will work to solve the issue for the participant(s) and subsequently determine how best to prevent this complication to future participants. Considerations for statistical implications of using these data are explained in Section 6.3.2 Statistical Considerations.

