### **Study Visit**

Study visits will take place at the CHOP Roberts Center for Pediatric Research and will not exceed 90 minutes. The following events will take place at the study visits:

Click tight technology explanation by study staff

Initial car seat install- baseline

First misuse scenario

Study team assessment

Reaction Survey

Second misuse scenario

Study team assessment

Reaction Survey

Third misuse scenario

Study team assessment

Reaction Survey

Preference and Experience interview

Participant debrief

Provide participants with remuneration for time and effort

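### Could staff help for the first 10 or fewer participants coach the app arm between scored scenarios?

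*Protocol*

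**What the plan says.** Protocol section 3.1.2 (Study Treatment Phase) sets up an early check covering the first 10 or fewer participants. Incoming data are watched over the first few weeks, and when a complication with the technology or data collection appears, "we will work to solve the issue for the participant(s) and subsequently determine how best to prevent this complication to future participants". The example given is "not understanding how to read the indicator lights". The paragraph ends with a cross-reference: "Considerations for statistical implications of using these data are explained in Section 6.3.2 Statistical Considerations". That section is not in the text at hand.

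The same section says "There will be a one-time study visit". On the introduction it says "Next, the team member will explain the click tight car seat system and demonstrate it to the participant". Scoring includes "asking the participant to see the app once they are finished the scenario". The Study Visit list opens with "Click tight technology explanation by study staff", and after each of the three scenarios it has "Study team assessment" followed by a reaction survey. Under Allocation to Treatment Groups and Blinding, each scenario is done once.

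Section 5.2.3 (Harness Installations & Assessments) counts lights for the intervention seat only. For every scenario it also records time, observed difficulties and remaining errors.

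**The concern.** Solving the problem for the affected participant is named as a separate step, before prevention for later participants, and no time is set for it. With a single visit and each scenario done once, help for that person could fall between two scored scenarios, and an unaided result lost in this way cannot be obtained again.

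The lights belong to the intervention seat, so explaining them would reach one arm only. The introduction, as described, names the click tight system and not the lights or the app, so such an explanation might go beyond what every participant receives. Failing to understand the lights is also something the study would want to observe. If staff corrected it after scenario 1, later tightness, time and errors in the app arm could look better than they would without help, and the comparison would lean towards the app.

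**Working it through.** The protocol gives no alpha, power, error rate or allocation ratio, so there is no figure of its own to reproduce. The check has two parts: what the text fixes, and how large the effect could be if the worrying reading were true.

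**What the text fixes**

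- *Scoring order.* The Study Visit list puts the team's assessment directly after each scenario, and section 3.1.2 has the app inspected when the scenario is finished. The early-phase paragraph says that these procedures will be evaluated, not that they are suspended. The scenario in which a problem first shows is therefore scored before anything that follows it, and the problem can be recorded as an observed difficulty under section 5.2.3.
- *What remains open.* Only carry-over into scenarios 2 and 3, and only if help is given between scenarios.
- *Whether such help is stated.* It is not. Watching data over several weeks and fixing faults in the technology or data collection also describes troubleshooting at study level. Help within the visit is an inference from there being one visit.

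**Exposure**

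Inputs: at most 10 early participants (section 3.1.2); about 100 enrolled and at least 90 evaluable (Total Number of Subjects Projected); three scenarios each.

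- Participants: 10/100 = 10.0% of enrolled, 10/90 = 11.1% of evaluable.
- Assessments exposed by help after scenario 1: (10 × 2)/(90 × 3) = 20/270 = 7.4%.

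This is a ceiling, because it takes every early participant to be helped.

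**Size under assumptions**

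Assumed, not in the protocol: 1:1 allocation with 45 evaluable per arm; a binary error outcome with true rate 0.5 in both arms; k app-arm participants helped, with their error rate either halved to 0.25 or reduced to 0; helped data analysed as usual.

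Shift in the app-arm error rate in one later scenario = k × (0.5 − new rate)/45:

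- k = 1: 0.25/45 = 0.56 to 0.5/45 = 1.11 percentage points.
- k = 5: 1.25/45 = 2.78 to 2.5/45 = 5.56 percentage points.

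Averaged over three scenarios with help after the first, multiply by 2/3: 0.37 to 0.74 points (k = 1) and 1.85 to 3.70 points (k = 5).

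False-positive rates come from exact enumeration of the pooled two-proportion z test at two-sided 5%, for one later scenario. The lower figure is for help that halves errors, the higher for help that removes them:

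| Helped (k) | Favouring the app | Two-sided total |
|---|---|---|
| 0 | 2.25% | 4.5% |
| 1 | 2.5% to 2.8% | 4.5% |
| 3 | 3.2% to 4.3% | 4.7% to 5.2% |
| 5 | 4.0% to 6.5% | 5.1% to 7.0% |

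For k = 5 at other assumed error rates, the chance of a false result favouring the app is 3.9% to 5.5% at a rate of 0.3 and 6.0% to 11.2% at a rate of 0.7, against 2.7% with none helped at either rate.

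Under an even split, five helped means every early app-arm participant. If helped data are set aside in the analysis, the inflation disappears and only some unaided results are lost.

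**The case for a change.** The best case for a change is that the timing of staff help is conduct of the visit, not analysis. Two staff members could follow the paragraph faithfully and act differently: one might explain the lights after scenario 1, the other wait until the end. An analysis rule can drop helped results only if someone recorded which ones they were, and no passage asks for such a log specifically. Dropping them would not restore the unaided result either. The statement under Potential Benefits of Participation that participants get no custom feedback on their harness installation does not settle the matter, because it does not mention the lights or the app and concerns the end of the visit. A clarifying sentence would cost almost nothing.

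Much of this stands: the wording is open, and a sentence or a line in the staff procedures would be reasonable housekeeping. It does not show that following the protocol as written gives a wrong result. A rule to score before helping would repeat the Study Visit order. Holding every explanation until the third scenario is scored is one choice; allowing help, logging it by participant, arm and scenario, and handling it by a rule set in advance is another. That the introduction omits the lights is read from a short description and a list of headings. Losing a few unaided results is also a fair price for an early phase meant to find unforeseen problems.

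**Conclusion.** No change is needed. The protocol is silent on when early help is given, but it neither contradicts itself nor prescribes coaching between scenarios. The feared bias needs three things together: help within the visit, enough app-arm participants helped to matter, and their later data analysed unchanged. The first is an inference. The second is limited to the first 10 or fewer participants, and with one helped the two-sided error rate does not move. The third cannot be presumed, because the protocol recognises the issue and refers it to Section 6.3.2, which could not be read here and is not criticised.

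The larger figures, such as 5.1% to 7.0% two-sided, need all five early app-arm participants under an even split to be helped, and their upper ends need help to remove every error. They rest on the assumed 1:1 allocation, binary outcome and 50% error rate; a 70% error rate would make the worst case larger. Confidence that no material harm follows is reasonable rather than complete, because the handling of these data is unseen.

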### Allocation to Treatment Groups and Blinding

This study will use a control and intervention group. Each enrolled participant will experience each of the three misuse scenario's once.

## **Study Duration, Enrollment and Number of Sites**

### **Duration of Study Participation**

Enrolled participants will be asked to complete one online intake survey, lasting up to 20 minutes, and one study visit, which may last up to 90 minutes, including their post-installation interview.

### **Total Number of Study Sites/Total Number of Subjects Projected**

CHOP is the only investigative site for this research study.

It is expected that approximately 100 participants will be enrolled to produce at least 90 evaluable participants.

### **Study Population**

We will seek to recruit at least 25% fathers and ensure a diverse sample of socioeconomic and racial diversity.

### **Inclusion Criteria**

#### Participant/Guardian

- 1) Males or females age 18 to 75 years
- 2) Has harnessed/fastened a child into a car seat in the last 5 years
- 3) Valid drivers license

### **Exclusion Criteria**

#### Participant

- 1) Participant is not fluent in written and/or spoken English
- 2) Participant cannot install a safety seat due to a physical limitation

## **STUDY PROCEDURES**

### **Pre-study Visit**

### **Screening/Verbal Consent**

A member of the research team will begin by explaining the study to the participant. The participant will be asked if they are interested in participating in the study. If interested, the screening questionnaire will be administered to determine eligibility. Eligible participants will be asked to consent to study procedures.

### **Self-administered Intake Survey**

Participants will receive an invitation to complete the intake survey at their convenience, prior to their study visit. Participants will receive both email and phone reminders if the survey has not been completed in advance of their scheduled study visit. The intake survey will be hosted within REDCap. If participants have not completed this intake survey prior to their study visit, they will be asked to complete the survey in-person before moving on to the intervention phase.

### **Study Visit**

Study visits will take place at the CHOP Roberts Center for Pediatric Research and will not exceed 90 minutes. The following events will take place at the study visits:

Click tight technology explanation by study staff

Initial car seat install- baseline

First misuse scenario

Study team assessment

Reaction Survey

Second misuse scenario

Study team assessment

Reaction Survey

Third misuse scenario

Study team assessment

Reaction Survey

Preference and Experience interview

Participant debrief

Provide participants with remuneration for time and effort

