### 5.1.4 Intake Survey

All participants will complete an intake survey that will collect data on a variety of car seat measures - current use, behaviors, knowledge, and preferences; and basic sociodemographics. Measures will include:

- Age (years)
- Sex
- Race/Ethnicity
- Self-reported crash history of self
- Household income
- Previous experience installing safety seats and harnessing children into them
- Risk perceptions about child occupant safety
- Barriers and facilitators to safety seat use
- Knowledge and attitudes about existing child occupant safety programs and policies

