### Efficacy Evaluations

#### 5.2.3 Harness Installations & Assessments

Each participant will complete three (3) misuse scenarios using child safety seats during the study visit.

The assessment of each misuse scenario (n=3) will capture the following information:

Method of harness (e.g., direction of pull to tighten, if the participant checks the tightness or makes adjustments, if participant asks child about tightness)

Length of time (in seconds) to harness

Tightness of harness in control seat (measured by a load cell and pinch test)

Tightness of harness in intervention seat (measured by the number of lights achieved in tensioning, a load cell and pinch test)

Difficulties observed (e.g., participant is unable to get child to cooperate, participant is unable to tighten harness because of physical limitations, or angle of seat makes it difficult to harness child)

Errors present at end of scenario

A series of questions for the participant on their experience during the scenario

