## **STUDY ADMINISTRATION**

### **Treatment Assignment Methods**

#### **Randomization**

Participants will be randomly assigned to either the intervention group or control group upon their arrival to the study visit. The randomization sequence was generated using SAS software, version 9.4 (SAS Institute, Cary, NC, USA).

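### Is it a flaw that every participant does an install called baseline, yet no assessment of it is specified?

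*Protocol*

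**What the plan says.** Section 3.1.2 (Study Treatment Phase) has a staff member explain and demonstrate the click tight system. Next: "The participant will then be asked to do a full install of the car seat prior to completing the misuse scenarios". The Study Visit section lists this step as "Initial car seat install- baseline". In that list a study team assessment and a reaction survey follow each of the three misuse scenarios; neither follows the install.

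Section 5.2.3 sets the scope of measurement: "The assessment of each misuse scenario (n=3) will capture the following information". The items include time to harness, harness tightness (load cell and pinch test, plus the number of lights in the intervention seat) and "Errors present at end of scenario".

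On the contrast between groups, section 3.1.2 says: "Participants in the intervention group will use the app while participants in the control group will complete the scenarios without the app". On timing, the same section says "Once the participant is enrolled, they will be allocated to either the control or intervention group", while the Randomization section has participants "randomly assigned to either the intervention group or control group upon their arrival to the study visit". Under either statement, allocation comes before the install.

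Data collected before the visit come from the intake survey (section 5.1.4), which covers "current use, behaviors, knowledge, and preferences; and basic sociodemographics" and also previous experience of installing seats and harnessing children.

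**The concern.** To a statistician, baseline normally means a measurement taken before the intervention and available for adjustment. Here the step carries that name, everyone performs it, and staff are in the room, yet the text at hand names no measure, form or use for it. The intake survey gives answers about experience and knowledge, not observed performance.

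If the install really goes unrecorded, no analysis plan can recover it later. In a trial expecting at least 90 evaluable participants, a good prognostic covariate could noticeably tighten the estimate. At stake would be precision only. Randomisation already protects the comparison from bias, so an unmeasured baseline leaves it unbiased.

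**Working it through.** **1. Is anything stated wrongly or contradicted?** The three places agree. Section 3.1.2 says the misuse scenarios are evaluated, the Study Visit list puts assessments after the scenarios, and section 5.2.3 confines its list to the three scenarios. No place promises a baseline score that another omits. Whether to adjust for a covariate belongs to the analysis plan, which is not at hand. Nor is Section 6.3.2 (Statistical Considerations), to which section 3.1.2 refers.

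**2. What could be gained?** The only figures in the protocol are about 100 enrolled and at least 90 evaluable. These fit a 10% loss, 90 / (1 − 0.10) = 100, but the 10% is itself inferred from the two numbers, so this is only a consistency check.

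Assumed, because the text at hand does not give them: 1:1 allocation (45 per group), two-sided 0.05, 80% power, a single outcome, and a correlation ρ between baseline score and outcome.

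- Unadjusted detectable difference: (1.960 + 0.842) × √(2/45) = 0.591 SD.
- Cost of estimating one covariate: (90 − 3)/(90 − 4) = 87/86 = 1.0116.
- Net variance ratio: (1 − ρ²) × 87/86.
- Break-even: ρ = √(1 − 86/87) = 0.107.

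| ρ | Net variance ratio | Detectable difference (SD) | Power at 0.591 SD |
|---|---|---|---|
| 0 | 1.012 | 0.594 | 79.5% |
| 0.2 | 0.971 | 0.582 | 81.1% |
| 0.3 | 0.921 | 0.567 | 83.1% |
| 0.5 | 0.759 | 0.514 | 89.6% |
| 0.7 | 0.516 | 0.424 | 97.4% |

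For a yes/no outcome such as the pinch test with pass rate p, taking ρ on an assumed underlying normal scale, the usable correlation is ρ × φ(z_p)/√(p(1 − p)). The factor is 0.798 at p = 0.5 and 0.585 at p = 0.9. The net fall in variance is 1 − (1 − (factor × ρ)²) × 87/86:

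- p = 0.5: 4.6% at ρ = 0.3 and 14.9% at ρ = 0.5; break-even ρ = 0.107/0.798 = 0.134.
- p = 0.9: 2.0% at ρ = 0.3 and 7.5% at ρ = 0.5; break-even ρ = 0.107/0.585 = 0.183.

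**3. Where would ρ lie?** The protocol does not say, but three features point away from the high end.

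- The install comes straight after a demonstration, which may push most participants towards a correct result and leave little spread.
- Installing a seat and tightening a harness are different tasks.
- The comparator above is an unadjusted analysis. If the analysis uses the experience items from the intake survey, the relevant ρ is the partial correlation given those items, which is typically smaller.

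**4. Would scoring be simple?**

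- The time, load cell and pinch test items in section 5.2.3 concern harnessing, and the error item refers to the end of a scenario. Section 3.1.2 describes an install of the seat, and nothing shown says that a doll is harnessed at that step. A separate installation form would be needed.
- The section Potential Benefits of Participation states that not all study team members are certified Child Passenger Safety Technicians, so reliable scoring of an installation cannot be taken for granted.
- Allocation precedes the install. A score could serve as a baseline covariate only if seat, app and light feedback were the same in both groups. Section 5.2.3 distinguishes a control seat from an intervention seat. If these are physically different, one group would install a seat it does not then use, and the groups would begin the scenarios with unequal familiarity.

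**The case for a change.** The best argument for the concern is that what staff record at a visit is protocol content, not analysis plan content. On that view a step named baseline is either a measurement, and should have a measure, or practice, and is misnamed. The possible loss from adjusting is small (about 1.2% in variance at ρ = 0) and the possible gain is real (power from 80% to 89.6% at ρ = 0.5).

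Part of this stands. The reading of the text is correct, the arithmetic holds, and the protocol does leave open whether and how the install is recorded. But that is a missing detail or a matter of wording, not a wrong statement. The word baseline is as compatible with a recorded step as with an unrecorded one, the Study Visit section is a bare list of events, and other parts of the plan are not at hand. The efficacy section as shown starts at 5.2.3; since numbering is irregular elsewhere this proves nothing, but it is a further reason not to treat silence as omission. The argument that little can be lost also counts only the covariate's cost in variance. It leaves out the new form, the scoring reliability and the possible seat change.

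**Conclusion.** The concern does not hold. The protocol is consistent on this point, and the comparison between groups is valid with or without a scored baseline install. Adding one would be an optional design preference. With 90 evaluable participants split equally and a continuous outcome, its effect on variance runs from a 1.2% loss at ρ = 0 to falls of 7.9% at ρ = 0.3 and 24.1% at ρ = 0.5. For a yes/no outcome with a 90% pass rate the falls are 2.0% and 7.5% at those two correlations. Every one of these figures rests on an assumed ρ and an assumed 1:1 allocation; only the 90 comes from the protocol. Against this uncertain gain stand measures that do not fit the task and conditions that might disturb the comparison itself. The residue is an ambiguous label, which does not affect the validity of any result.
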